#### 6.1.1 Sample and population of the study

This research will be carried out at one prison unit, located in the city of Dourados, in the state of Mato Grosso do Sul. Currently, this prison unit has approximately 2,300 inmates, with a mean age of  $31.5 \pm 9.4$  years; an average of  $9.7 (\pm 4.2)$  individuals per cell, who remain in a closed regimen, about  $20.8 (\pm 24.1)$  months. The TB indicators show a tuberculin test seroconversion rate of 26% (23-26) and incidence, 2.45 / 100,000(28).

The sample was calculated for a significance level of 5%, detection power of 90%, considering a percentage of occurrence of latent TB of 20% in the control group after one year of follow-up and 10% in the experimental group. For these parameters, 560 individuals will be needed for the study, however, 30% will be added for possible losses, ending the sample in 728 participants. Memory calculation available at <https://www.sealedenvelope.com/power/binary-superiority/>.

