#### 6.1.2 Randomization and masking

Two groups, called intervention (INH) and control (placebo), respectively, each composed of 364 participants, will be formed from a simple randomization process using the True Random Number Service developed by the School of Computer Science and Statistics in Dublin, Ireland and available at <[www.random.org](http://www.random.org)>. The sequence generator mode used by the principal investigator will produce 728 random alpha-numerical codes, composed of three digits each, that will be delivered to the pharmacist for individual randomization (intervention vs control) containing only the identifying code.

The study pharmacist will be responsible for randomization of the participants and organization of INH-containing bottles or placebo for dispensing during DOT visits. As this is a double-blind study, the other team members are blind and do not have access to the randomization list. The study participants will also not know in which group they are allocated. The description of the pharmacist's activities in the clinical trial are detailed in specific SOP.

The use of placebo was a strategy because there is no clinical trial of primary prophylaxis for TB.

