## 6.7 Interim analysis

After a 6-month visit of at least 100 participants, in addition to the follow-up clinic-laboratorial evaluation (which includes blood collection for hepatic enzyme dosage and directed clinical examination), an evaluation of the effectiveness of the intervention will be carried out, through sputum culture and interferon-gamma dosing / quantification. It is estimated that there is a linear relationship between follow-up time and the risk of acquisition of latent TB.

This evaluation intends to verify the feasibility of continuity of the study and adequacy of the sample calculation. The study will be discontinued if the primary endpoint is less than 2.5% as compared to the control group, or if the difference between the intervention group and the control group is greater than 12.5% according to the box below:

	Intervention (isoniazid) (N=162)	Control (placebo) (N=162)	Finale total number (N final+30%)
Reference	5.0%	10%	726
Insufficient sample	7.5%	10%	3357
Insufficient sample	10.0%	12.5%	3910
Insufficient sample	12.5%	15.0%	4555
Insufficient sample	15.0%	17.5%	5114
Insufficient sample	17.5%	20.0%	5361
Sufficient sample	5.0%	17.5%	172
Sufficient sample	7.5%	20.0%	187
Sufficient sample	10.0%	22.5%	213
Sufficient sample	12.5%	25.0%	218
Sufficient sample	15.0%	27.5%	229

Figura 2 - Sample table of the sample values in both groups (intervention and control), based on the primary outcome.

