## 6.9 Ethical aspects

Following the provisions of Resolution 466/12 of the National Health Council, the present study was sent to the IRB of the UEMS, having its first approval in the Opinion no. 1,677,965, CAAE no. 57333716.8.0000.8030.

This study will use REDCap to capture data and it will be used as a source document of the information contained in it. A copy of the completed document will be printed and archived in the participant's folder.

It is registered and approved in the Brazilian Registry of Clinical Trials, available at <<http://www.ensaiosclinicos.gov.br/rg/RBR-4n67h3/>> and in the Clinical Trials, available at <<https://clinicaltrials.gov/ct2/home>>, identifier NCT03028129.

All individuals approached by the researcher and team should read and sign the TCLE to participate in the research.

During the course of the experiment, participants will be monitored clinically and laboratorially for the occurrence of adverse effects, particularly hepatotoxicity, a more frequent event (1%) according to the literature(33).

If the intervention results in greater than expected benefit, the team will discontinue the experiment and provide all participants with INH treatment.

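### The interim stop for benefit in section 6.7 needs a gap above 12.5 points, but its own Reference row expects only a 10% control risk at 6 months, so even a fully effective drug would usually not trigger it; the rule also has no test and no settled sample size

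*Combined protocol and SAP*

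**What the plan says.** Section 6.1.1 sizes the trial on latent TB: "The sample was calculated for a significance level of 5%, detection power of 90"%, with "20% in the control group after one year of follow-up and 10% in the experimental group". The total is 560, or 728 with the 30% allowance for losses.

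Section 6.7 assumes that risk accrues linearly with follow-up. It places one look "After a 6-month visit of at least 100 participants" and ends the study if the gap is too small or "if the difference between the intervention group and the control group is greater than 12.5% according to the box below". The box (Figura 2) is headed "Intervention (isoniazid) (N=162") and likewise 162 for control. Its Reference row is 5.0% v 10%. Its five Sufficient sample rows each show a gap of exactly 12.5 points, with control risks from 17.5% to 27.5%. No test, significance level or confidence limit is attached to the stop.

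Section 6.9 adds: "If the intervention results in greater than expected benefit, the team will discontinue the experiment". Section 6.6 analyses the relative risk with a 95% CI and does not mention the look.

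**The concern.** A benefit threshold should be reachable, with good probability, by a drug much better than planned, under the risks the plan itself expects. Here it lies above the whole expected control risk. The observed gap can exceed 12.5 points only if control conversions run above the planned 10%, whether by chance or because the true risk is higher. A highly effective drug would then usually be continued against placebo past a look that section 6.9 implies should catch it.

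The threshold is also a bare difference. The evidence behind a 12.5-point gap depends on the number of participants and the event rate, and the section gives two sizes: at least 100 in the text, 324 in the box. At the smaller size the trial could end, before the 12-month primary endpoint is complete, on a gap that the trial's own analysis would not call significant.

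**Working it through.** **Inputs.** 12-month risks 20% v 10%, 5% significance, 90% power, total 560 (6.1.1); linear accrual, Reference row 5% v 10%, stop above 12.5 points, 100 participants or 162 per arm (6.7); background rate 26% (6.1.1; called annual in section 3). Assumptions: two-sided tests, 50 per arm at 100 participants, and 12.5% read as absolute percentage points, as the box rows imply.

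**1. The plan's own figures.** The pooled two-proportion formula for 20% v 10% at 90% power gives 532 in total; with continuity correction, 572. The stated 560 is 2.1% below the latter, and 560 × 1.3 = 728.

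**2. The box shows 6-month risks.** Doubling the Reference row to 10% v 20% and applying the corrected formula gives 572 × 1.3 = 744, close to the printed 726. Using 5% v 10% undoubled gives 1,615. So 10% is the expected control risk at the look, and the largest possible true gap is 10 − 0 = 10 points.

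**3. Chance of stopping for benefit.** With X_c ~ Bin(n, p_c) and X_i ~ Bin(n, p_i), P(stop) = P[(X_c − X_i)/n > 0.125], computed exactly. The smallest firing gap is 7 participants at n = 50 (50 × 0.125 = 6.25) and 21 at n = 162 (162 × 0.125 = 20.25). For a fully effective drug this reduces to P(X_c ≥ 7) = 0.230 and P(X_c ≥ 21) = 0.131.

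| 6-month risk, INH v control | 50 per arm | 162 per arm |
|---|---|---|
| 0% v 10% (fully effective) | 23% | 13% |
| 2% v 10% (80% effective) | 14% | 4% |
| 5% v 10% (planned) | 6.4% | 0.5% |
| 10% v 10% (no effect) | 1.5% | 0.01% |
| 0% v 13% (26% a year, halved) | 48% | 54% |
| 0% v 15% | 64% | 80% |

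**4. Strength of evidence when it fires.** At 50 per arm, the smallest firing gaps give:

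| INH v control | Chi-square p | Fisher p |
|---|---|---|
| 0 v 7 | 0.006 | 0.012 |
| 2 v 9 | 0.025 | 0.051 |
| 3 v 10 | 0.037 | 0.071 |
| 5 v 12 | 0.062 | 0.108 |

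For 3/50 v 10/50, RR = 0.30 and SE(log RR) = √(1/3 − 1/50 + 1/10 − 1/50) = 0.627, so the 95% CI is 0.09 to 1.03.

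Among outcomes that fire at 50 per arm, the share with p ≥ 0.05 is 0.3% by chi-square and 21% by Fisher when the risks are 5% v 10%. At 15% v 27.5% the shares are 29% and 46%. At 162 per arm no firing outcome had p ≥ 0.05 at the rates examined.

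**5. False-benefit error.** Simulated with a look at 50 per arm, a final RR interval at 280 per arm and no drug effect, counting every early stop for benefit as a benefit claim. With both stops enforced as written, the one-sided rate is about 2.7% at 10% control risk (2.4% with no look) and about 4.6% at 15%.

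**The case against.** The strongest reply is that the look is described as a check on feasibility and on the sample-size calculation, that section 6.8 lets the team end the study at its discretion, and that section 6.9 separately commits to stopping for greater than expected benefit. A very effective drug is therefore not locked into running on. That stands as a limit on the consequences. It does not repair the rule: 6.7 states a numerical threshold on which the study will be discontinued, and team discretion is no substitute for a correct one.

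The first limb also rests on the Reference row. If the true control risk were 15%, a fully effective drug would stop in 64% to 80% of trials, and 6.1.1 itself quotes a 26% background rate. This is fair. A reader might infer that the threshold cannot be reached through efficacy at all; that is too strong, because observed gaps exceed true gaps by chance and the control risk may be higher than planned.

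A reader might also infer that the rule fails in both directions, with a serious risk of declaring an ineffective drug beneficial. The documents do not support that at the planned risk. The lower stop is mandatory as written and keeps the error near 2.7%, and 6.7 nowhere says that a stop is itself an efficacy claim. Nor is every gap that fires at 100 participants weak: 3/50 v 10/50 is significant by chi-square and not by Fisher. Finally, at least 100 is a minimum, which a look at 324 would satisfy.

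**Conclusion.** The concern holds in this form: the benefit threshold does not match the risks that its own box expects. At the planned 10% control risk a fully effective drug stops the trial in only 13% to 23% of cases, which sits badly with section 6.9. At 13% control risk the figure is about half.

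The secondary point is narrower. The rule has no allowance for sampling error and two inconsistent sizes. At about 50 per arm it can fire on gaps not significant at 5%, mainly when event rates are high or when Fisher's test or the RR interval is used. Inflation of false-benefit error is about 0.3 points at the planned risk and about 2 points at 15% (4.6% against 2.4%).

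These figures assume equal arms at the look, linear accrual as stated, and the upper limit read as a stop for benefit. The 6.7 wording gives no direction; 6.9 and the Sufficient sample rows supply it.

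**What to change.** In 6.7, replace the 100-participant minimum with the box's own size: 324 participants with a 6-month IGRA, about 162 per arm. State it as a total, because simple randomisation does not guarantee equal arms. Replace the 12.5-point limit with a prespecified test-based boundary, for example Haybittle-Peto: stop for benefit only if the two-sided p-value is below 0.001. The final 95% CI in 6.6 then stays essentially valid. Refer to this boundary in 6.9.

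Exact stopping probabilities at 162 per arm, using Fisher p < 0.001:

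| 6-month risk, INH v control | Current rule | p < 0.001 |
|---|---|---|
| 0% v 10% | 13% | 94% |
| 2% v 10% | 4% | 34% |
| 5% v 10% | 0.5% | 3% |
| 10% v 10% | 0.01% | 0.03% |
| 15% v 27.5% | 49% | 25% |

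The change is to protocol wording only. There are two costs: the look comes later than 100 participants, and the trial stops less often than under the current rule when event rates are high, as the last row shows. Other test-based boundaries would also serve; what matters is that one is fixed in advance.

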## 6.8 Study interruption

The study may be terminated early according to the outcome of the interim analysis or at the discretion of the research team, which shall prepare written notices to the IRB and to the sponsor, detailing the reasons interruption of the study.

Participants should be informed about early termination of the study, treatment discontinued, and premature exclusion visit according to figure 1.

## 6.9 Ethical aspects

Following the provisions of Resolution 466/12 of the National Health Council, the present study was sent to the IRB of the UEMS, having its first approval in the Opinion no. 1,677,965, CAAE no. 57333716.8.0000.8030.

This study will use REDCap to capture data and it will be used as a source document of the information contained in it. A copy of the completed document will be printed and archived in the participant's folder.

It is registered and approved in the Brazilian Registry of Clinical Trials, available at <<http://www.ensaiosclinicos.gov.br/rg/RBR-4n67h3/>> and in the Clinical Trials, available at <<https://clinicaltrials.gov/ct2/home>>, identifier NCT03028129.

All individuals approached by the researcher and team should read and sign the TCLE to participate in the research.

During the course of the experiment, participants will be monitored clinically and laboratorially for the occurrence of adverse effects, particularly hepatotoxicity, a more frequent event (1%) according to the literature(33).

If the intervention results in greater than expected benefit, the team will discontinue the experiment and provide all participants with INH treatment.

## **6.10 Quality control**

Sponsor will provide monitoring visits that will include reviewing forms, batch counting of drugs, checking laboratory data, monitoring adverse events, and documenting any violations or deviations from the protocol.

This study may be subject to audit procedures in cases where the sponsor or the Brazilian regulatory agency (ANVISA) deems relevant.

## **6.11 Potential risks**

1) The protocol will identify active and latent cases of TB among inmates. Although the diagnosis of TB provides the prisoner with situations that can be understood as benefits, such as admission to less busy wards and access to better services, the disease in Brazil, as in many countries, is potentially stigmatizing.

2) During recruitment, cases of HIV and viral hepatitis (B and C) may be identified, which, although treatable, as well as TB, are potentially stigmatizing.

3) Participants allocated to the experimental group will receive INH. Mild and serious adverse events including hepatotoxicity may occur. All participants will be monitored every three months through clinical consultation and blood tests when necessary.

4) The study team will extract information about demographics, behaviors, and past medical history during interviews, so there is the potential risk of discomfort in answering questions and breach of confidentiality regarding personal information.

5) Blood samples will be collected by venipuncture during the study, which, despite having minimal risks, may be associated with discomfort and bruising.

6) Inmates are inherently vulnerable populations who may feel compelled to participate in the study and may perceive that their involvement in the proposed study provides benefits or risks in relation to the conduct of officials and other prisoners.

7) The study team is exposed to the risk of infections and work-related illnesses due to the high rate of TB transmission in the study sites (prison).

### **6.12 Expected benefits**

- 1) Reduce the risk of becoming infected with TB or developing the disease during incarceration.
- 2) Quantification of the risk / benefit of primary prophylaxis in subjects without tTB (active or latent), but strongly exposed to the risk of becoming infected with TB or developing the disease.
- 3) Produce scientific evidence to modify the recommendations of the competent organs regarding primary prophylaxis in the prison system.

